6.2.2 Per-Protocol Population

The Per-Protocol (PP) population is defined as the ITT population who did not experience a major protocol violation. Major protocol violations include, but are not limited to, subjects who:

- Entered the study although they did not satisfy the eligibility criteria
- Completed incorrect version of PROMIS based on age of subject
- Did not return to protective weight-bearing activities by 3 weeks (+3 days)
- Received Lapiplasty® Procedure (or other hallux valgus procedures) on contralateral foot less than 6 months after initial index procedure
- Developed withdrawal criteria during the study, but were not removed from study participation

All effectiveness, safety, and health economic outcomes analyses will utilize the ITT population. If the PP population and ITT population differ considerably, sensitivity analyses will be performed using the PP population.

6.3 Missing Data

Effectiveness and health economic analyses will be based on available data, without imputation for missing values. For Quality of Life outcomes (MOxFQ and PROMIS-29/PROMIS-25), missing data will be handled as specified in the Derived Variables section. For safety analyses, missing event dates will be imputed as follows:

- If only month and year are reported, then day is assigned as the 15th of the month
- If only year is reported, then month and day is assigned as July 1st

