## **3.0 STUDY ENDPOINTS**

### **Primary:**

Radiographic recurrence of hallux valgus deformity at 24 months for subjects with successful correction (defined as IMA <9.0°, HVA <15.0° and TSP as ≤ 3 at 6 weeks post-Lapiplasty® Procedure). Recurrence is defined by any two of the following three criteria being met at 24 months post-procedure: IMA of ≥12°, HVA ≥20° and TSP ≥4.

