##### **Investigator Decision**

If the subject experiences an adverse event or the Principal Investigator or Medical Monitor believes it is in their best interest to discontinue participation in the study for other reasons, they

will be withdrawn from the study.

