#### **Other (which may include):**

- Protocol deviation, noncompliance or violation;
- Sponsor recommendation;
- Device/index procedure failure, including subjects who had a previously unidentified medical history finding that made treatment with the Lapiplasty® Mini-Incision™ System unfeasible;
- Death.

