1.1 Objectives

- 1) To determine radiographic recurrence of hallux valgus and the timing of failure following hallux valgus correction with the Lapiplasty® Procedure.
- 2) To determine whether the Lapiplasty® Procedure effectively corrects anatomical alignment of the 1st metatarsal and sesamoids in all three planes.
- 3) To assess whether early weight-bearing (WB) after the Lapiplasty® Procedure affects the union rates or causes loss of 3-plane correction.
- 4) To evaluate the quality of life and pain scores following the Lapiplasty® Procedure.

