1.2 Endpoints

1.2.1 Primary Endpoint

Proportion of subjects with radiographic recurrence of hallux valgus deformity (bunion recurrence) at 24 months, limited to subjects with successful correction at 6 weeks.

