6.4.8 Recurrence

Recurrence (loss of correction) is considered to have occurred at 24-months post-procedure if any two of the following 3 criteria are met: IMA of $\geq 12^\circ$, HVA $\geq 20^\circ$, TSP ≥ 4 . An alternative definition of recurrence will also be applied: HVA $\geq 15^\circ$.

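### The primary recurrence proportion uses only available 24-month films, so corrected feet revised earlier can count as non-recurrent and feet that recurred and then exited drop out

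*SAP*

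**What the plan says.** **Endpoint.** SAP 1.2.1 defines the primary endpoint as "Proportion of subjects with radiographic recurrence of hallux valgus deformity (bunion recurrence) at 24 months, limited to subjects with successful correction at 6 weeks". Protocol section 3.0 has the same restriction: "Radiographic recurrence of hallux valgus deformity at 24 months for subjects with successful correction".

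**Scoring rule.** SAP 6.4.8: "Recurrence (loss of correction) is considered to have occurred at 24-months post-procedure if any two of the following 3 criteria are met". The criteria are IMA of at least 12°, HVA of at least 20° and TSP of at least 4. SAP 7.2.1 repeats the rule.

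**Missing data.** SAP 6.3: "Effectiveness and health economic analyses will be based on available data, without imputation for missing values". Protocol 9.5 agrees. The only sensitivity analysis of the primary endpoint (SAP 7.2.1) uses the per-protocol set, and only if that set differs considerably from ITT.

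**Revision and withdrawal.** Protocol 7.12 has secondary surgical interventions recorded with their reason. SAP 7.3.2 summarises them among complications and health economics. Protocol 4.2.5 lists reasons for leaving the study. One begins "If the subject experiences an adverse event or the Principal Investigator or Medical Monitor believes it is in their best interest to discontinue participation" and ends in withdrawal. Another begins "Device/index procedure failure, including subjects who had a previously unidentified medical history finding" and goes on to describe a finding that made treatment with the system unfeasible. The section also asks for final-visit observations at withdrawal.

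**Timing.** Objective 1 in SAP 1.1 is "To determine radiographic recurrence of hallux valgus and the timing of failure following hallux valgus correction with the Lapiplasty® Procedure". Films are centrally read at 6 weeks and at 4, 6, 12 and 24 months. SAP 7.2.2 plans recurrence percentages at 12 and 24 months.

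**The concern.** Recurrence is an event that can happen, and be treated, at any time after correction, but the plan measures it as a state at one visit. Two kinds of known failure are then misplaced.

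- A corrected foot that loses alignment and is revised at, say, month 10 may show good alignment at 24 months. Nothing tells the analyst to set that film aside, so the foot can be counted as a success.
- A corrected foot that meets the criteria at 12 months, after which the subject exits, has no 24-month film and leaves the proportion altogether.

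Non-union at 12 months (SAP 6.4.9; SAP 7.2.2, item 6) has the same weakness: a foot revised for non-union at month 8 can read as united at month 12.

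Both documents expect a low recurrence rate, so a handful of such feet is large relative to the count observed. What is at stake is the headline figure of the study and the answer to its first objective.

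**Working it through.** **1. The plan's own figures.** The sample size of 200 comes with no formula, dropout rate or target precision, so there is nothing to reproduce. The retrospective study cited in the introduction can be checked: 59/61 = 96.7% maintained correction and 1/61 = 1.6% had symptomatic non-union, both as stated. The complement, 2/61 = 3.3%, sets the order of magnitude used below.

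**2. How each foot is scored if the text is followed literally** (all corrected at 6 weeks)

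| Course of the foot | 24-month film | Scored as |
|---|---|---|
| Criteria met at 24 months, never revised | yes | recurrent |
| Revised for loss of correction, realigned | yes | non-recurrent |
| Revised for loss of correction, then exits | no | not in the proportion |
| Criteria met on an earlier film, then exits | no | not in the proportion |

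The last three rows are known failures, and none reaches the numerator.

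**3. Illustration.** All counts here are assumptions: 200 treated, 10 not corrected at 6 weeks, 20 lost for other reasons. That leaves 200 − 10 − 20 = 170 corrected feet with known status. Five are taken as recurrent at 24 months, and f is the number of early failures among the 170. Intervals are Clopper-Pearson 95%.

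- Early failures filmed after revision and scored as non-recurrent: 5/170.
- Early failures dropped: 5/(170 − f).
- Early failures counted as recurrent: (5 + f)/170.

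| f | Scored non-recurrent | Dropped | Counted as recurrent |
|---|---|---|---|
| 0 | 2.9% (1.0 to 6.7) | 2.9% | 5/170 = 2.9% (1.0 to 6.7) |
| 2 | 2.9% | 5/168 = 3.0% | 7/170 = 4.1% (1.7 to 8.3) |
| 4 | 2.9% | 5/166 = 3.0% (1.0 to 6.9) | 9/170 = 5.3% (2.4 to 9.8) |
| 8 | 2.9% | 5/162 = 3.1% (1.0 to 7.1) | 13/170 = 7.6% (4.1 to 12.7) |

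Dropping and misclassifying give almost the same answer; both miss the failures.

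**4. Other missing films.** With f = 4 counted as recurrent, adding back the 20 ordinary losses gives 9/190 = 4.7% if none recurred and 29/190 = 15.3% (10.5 to 21.2) if all did. The first lies below 5.3% and the second above it, so the direction for ordinary losses is open.

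**The case against.** The strongest reply is that the plan already shows much of this. SAP 7.2.2 and Table 3 report recurrence at 12 months by the same two-of-three rule. A foot recurrent at 12 months and lost afterwards is therefore counted there. Revisions appear in SAP 7.3.2 and Table 25, alignment change is summarised at 4 and 6 months, and Listing 5 gives the measurements. The schedule assesses secondary surgery through Visit 9, so follow-up after reoperation is expected. The study is single-arm and mainly descriptive, with no success threshold for the primary endpoint, so no prespecified conclusion would flip.

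This lowers the stakes but does not close the gap. The 12-month figure is a separate available-case snapshot that misses feet revised before it and cannot be combined with the 24-month figure into a cumulative rate. A table of complications does not change how the primary proportion is scored. The per-protocol analysis does not recover these feet either. It may remove more, because SAP 6.2.2 treats a subject who met withdrawal criteria but was kept on study as a major violation.

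Four stronger readings might be inferred, and the documents do not support them.

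- **That feet not corrected at 6 weeks are hidden failures of the primary analysis.** Their exclusion is the prespecified definition in both documents ("limited to subjects with successful correction at 6 weeks"), not an effect of the missing-data rule. A foot that was never corrected cannot recur, and the correction rate is reported in Table 4.
- **That the bias always favours the procedure.** This is true for known failures only (working, step 4).
- **That protocol 4.2.5 removes late procedure failures.** The only example given is a finding that made treatment unfeasible, and such a subject may never count as treated. Late loss of correction is a possible reading but not a stated one.
- **That timing of failure is not addressed at all.** Two recurrence time points are planned.

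**Conclusion.** The concern holds for corrected feet that fail before the 24-month film. Followed as written, SAP 6.3, 6.4.8 and 7.2.1 can score a revised foot as non-recurrent and drop a foot that recurred and then exited. For these feet the recurrence proportion is biased downward; for all missing films together the direction is unknown. The 12-month non-union endpoint shares the gap, and objective 1 is answered only in part, by two snapshots, although films are also read at 4 and 6 months.

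The size rests wholly on assumed counts. Four revised feet scored as non-recurrent would hide a move from 2.9% to 5.3%; none would change nothing. The illustration takes the 6-week correction status as given. The protocol joins all three correction criteria while the SAP asks for any two, a separate matter that affects who enters the primary set.

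A figure combining uncorrected, recurrent and revised feet among all treated would be larger, but it is a different estimand and does not measure bias in this one. The scoring rules should be settled before database lock.

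**What to change.** 1. **Scoring (SAP 6.4.8 and 7.2.1).** Do not use films taken after a revision. Count a corrected foot as recurrent if its first ray is revised for loss of correction before 24 months, or if its last film before revision or exit met the criteria. If the sponsor prefers to keep the protocol's 24-month definition, make this a prespecified, unconditional sensitivity analysis reported beside the primary figure.
2. **Timing.** Add a cumulative recurrence estimate over the 4, 6, 12 and 24-month films, interval-censored or Kaplan-Meier, with 95% CI. Define the event as the first film meeting the criteria, so that feet that exit and feet that stay are treated alike.
3. **Non-union.** Count revision for non-union before month 12 as non-union.
4. **Other missing 24-month films.** Report best-case and worst-case bounds.
5. **Withdrawal reasons.** Reconcile the adverse-event and procedure-failure reasons in protocol 4.2.5 with the 24-month endpoints, as regards continued data collection in consenting subjects.
6. **Optional.** Report an all-treated composite (not corrected, recurrent or revised) as a supplementary estimand.

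**Cost.** SAP wording, some programming and one protocol clarification, using films and intervention records already collected. Putting item 1 into the primary definition also changes the protocol's primary endpoint and needs an amendment; the sensitivity-analysis route does not. The reported rate may be less favourable.

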### **9.5 Missing Data**

Efficacy and health economic analyses will be based on available data, without imputation for missing values. For the Quality of Life outcomes, missing data will be handled as specified in the PROMIS-29, PROMIS-25 and MOXFQ scoring manuals. For safety analyses, missing event dates will be imputed as follows:

- If only month and year are reported, then day is assigned as the 15th of the month

- If only year is reported, then month and day is assigned as July 1st

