## **9.6 Interim Analyses**

Interim analyses will be performed during the study according to patient enrollment and availability of data of interest. Interim analyses will be used to provide early information about the safety and efficacy of the procedure and may be used for internal decision making, hypothesis generation, abstraction/publication for major orthopedic conferences, or other purposes, as applicable. Interim analyses will follow the methods in the statistical analysis plan.

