⁸ For the purposes of determining IMA, HVA and MMA for subject eligibility, measurements will be made according to institutional SOC. For the purposes of all data analysis, measurements made by the Central Radiologist will be utilized. If there are minor differences in baseline IMA, HVA and MMA measurements made by the central radiologist, the measurements of the PI/site will remain acceptable for determining subject eligibility.

⁹ Confirm exclusion criterion “subject is not a current nicotine user” prior to start of anesthesia. If subject indicates current use of nicotine, subject should be considered a screen failure.

¹⁰ If subject requires an incision >4.0 cm to complete the Lapiplasty® Procedure, the subject should be considered a screen failure.

¹¹ Documentation for return to weight bearing activities include time to start weight-bearing in boot, time to start weight-bearing in shoe, and time to full unrestricted activity.

¹² ROM - dorsiflexion and plantarflexion should be measured while subject is passive and non-weightbearing with the study provided goniometer.

¹³ Secondary surgical interventions, Wound healing requiring intervention, infection requiring intervention, hardware removal, revision procedure of 1st ray, other complication requiring surgical intervention.

¹⁴ Only AEs related to the Lapiplasty® Index Procedure or the Lapiplasty® System Implants will be recorded on the eCRF.

¹⁵ Radiographic Measurements are completed by the Central Radiologist only.

¹⁶ Healthcare Economic Outcomes, see Secondary Endpoints for data to be recorded on eCRF.

Sample Size

There is no formal sample size calculation as this is a single arm study and is descriptive in nature. A sample size of 200 patients is chosen, ensuring the feasibility of the study as clinical findings suggest that the bunion recurrence rate after the Lapiplasty® Procedure is low.

6 General Analysis Considerations

All analyses will be performed using SAS software, version 9.4 (SAS Institute Inc., Cary, NC).

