6.4.2 Change from Baseline

Change from baseline will be determined for ROM, VAS, PROMIS, MOxFAQ, and radiographic measurements (IMA, HVA, tibial sesamoid position (TSP), sagittal plane). It will be calculated as value at timepoint of interest minus value at baseline.

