6.4.9 Non-union

Non-union is defined as pain at the TMT joint plus one or more of the following: lucency, hardware failure, or recurrence.

7 Statistical Analysis

All continuous variables will be summarized using the following descriptive statistics: n, mean, standard deviation, median, minimum, maximum, and where appropriate 95% confidence intervals (CIs). The frequency and percentages of observed levels will be reported for all categorical measures. In general, all summary tables will be annotated with the total population size relevant to that table, including any missing observations. Data listings will be sorted by site, subject, and when appropriate by visit type within subject.

Two-sided T-tests will be generated for change from baseline analyses. P-values ≥ 0.001 will be reported to 3 decimal places; p-values less than 0.001 will be reported as “ <0.001 ”. P-values less than 0.05 will be considered statistically significant. The mean, standard deviation, and any other statistics other than quantiles, will be reported to one decimal place greater than the original data. Quantiles, such as median, or minimum and maximum will use the same number of decimal places as the original data. Estimated parameters, not on the same scale as raw observations (e.g. regression coefficients) will be reported to 3 significant figures.

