7.2.2 Secondary Effectiveness Analysis

Effectiveness analyses will be performed on the following secondary endpoints:

- 1) Percentage of subjects with recurrence at 12 months where recurrence is defined as meeting 2 of the following 3 criteria: IMA of $\geq 12^\circ$, HVA $\geq 20^\circ$ and TSP ≥ 4 .

- 2) Percentage of subjects with recurrence at 12 months and 24 months where recurrence is defined as HVA >15°.
- 3) Percentage of subjects with recurrence at 12 months and 24 months where recurrence is defined as HVA >20°.
- 4) Percentage of subjects with successful correction at 6 weeks.
- 5) Change from baseline in radiographic angular/positional alignment for HVA, IMA, TSP, and sagittal plane at 6 weeks, 4 months, 6 months, 12 months, and 24 months.
- 6) Percentage of subjects with non-union (absence of clinical/radiographic healing) at 12 months.
- 7) Time to weight-bearing in a controlled ankle motion (CAM) boot, in days.
- 8) Time to weight-bearing in shoes, in weeks.
- 9) Time to return to full unrestricted activity, in months.
- 10) Change from baseline in pain at the base of the big toe (bunion related) assessed via VAS at 0-14 days, 14-21 days, 6 weeks, 4 months, 6 months, 12 months, and 24 months.
- 11) Change from baseline in Quality of Life at 6 months, 12 months, and 24 months as measured by PROMIS-29 (for adult subjects), PROMIS-25 (for pediatric subjects), and MOxFQ (for all subjects).
- 12) Change from baseline in range of motion of the 1st MTP dorsiflexion, plantarflexion, and dorsiflexion plus plantarflexion at 4 months, 6 months, 12 months, and 24 months.
- 13) Change from baseline in foot swelling measurements at 0-14 days, 14-21 days, 6 weeks, 4 months, 6 months, and 12 months.
- 14) Summary of POSAS responses over time at 4 months, 6 months, 12 months, and 24 months.

Statistical summaries will be produced in accordance with section 7, and listings will be generated by site, subject, and visit (where applicable) within subject.

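### Continuous changes from baseline are tested visit by visit in whoever attended; a repeated-measures likelihood model beside those tables would remove the bias if drop-out depends on earlier observed scores, but not otherwise

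*SAP*

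**What the plan says.** SAP 6.3 sets the missing-data rule: "Effectiveness and health economic analyses will be based on available data, without imputation for missing values". Protocol 9.5 says the same: "Efficacy and health economic analyses will be based on available data, without imputation for missing values".

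SAP 6.4.2 defines change from baseline: "It will be calculated as value at timepoint of interest minus value at baseline". A subject needs both values to count at a visit. SAP 7 adds that "Two-sided T-tests will be generated for change from baseline analyses" and that "P-values less than 0.05 will be considered statistically significant".

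SAP 7.2.2 applies this at several post-operative visits: radiographic alignment at five (item 5), pain at seven (item 10, "assessed via VAS at 0-14 days, 14-21 days, 6 weeks, 4 months, 6 months, 12 months, and 24 months"), quality of life at three (item 11), range of motion at four (item 12) and swelling at six (item 13).

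No repeated-measures model and no missing-data sensitivity analysis is specified. The only sensitivity analysis is the per-protocol one in SAP 6.2.2 and 7.2.1, which does not address missed visits. On interim looks, protocol 9.6 says: "Interim analyses will follow the methods in the statistical analysis plan".

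**The concern.** Each row of a by-visit table can describe a different set of subjects. Someone with a poor 12-month pain score who misses month 24 adds nothing to the 24-month mean, although the earlier score says something about the likely later one. If the subjects who leave tend to be doing worse, the 24-month mean change looks too good, and part of the apparent trend is a change in who is being measured. If satisfied subjects are the ones who skip, the error runs the other way.

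The documents make outcome-related exit plausible. Protocol 4.2.5 lists withdrawal after an adverse event or by investigator decision, and failure of the device or index procedure, among the exit reasons. In addition, SAP 6.4.5 leaves a PROMIS short form unscored when any item is blank, so the analysed set can differ between domains at the same visit.

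Objectives 2 and 4 (alignment; pain and quality of life) are reported largely through these changes, and objective 3 (loss of correction) depends on comparing visits.

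**Working it through.** **Figures in the plan.** There is nothing to reproduce. The SAP says "A sample size of 200 patients is chosen, ensuring the feasibility of the study", with no SD, correlation or drop-out rate. Apart from n=200, every input below is an assumption.

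**Formula.** Let r_f be the correlation between the 12- and 24-month scores, r_b the correlation of baseline with either of them, and SD the common standard deviation. Let drop-out before month 24 depend on the 12-month score, and let m be the mean standardised 12-month score of those who stay. Under joint normality, those who stay have a 24-month mean shifted by r_f × SD × m and a baseline mean shifted by r_b × SD × m. Hence

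bias of the available-case mean change = SD × (r_f − r_b) × m.

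With logistic drop-out, m = −ln(odds ratio per SD) × E[p(1−p)] / (share retained), where p is the drop-out probability and E[p(1−p)] is found by numerical integration.

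- Strong case (25% missing, odds ×2): m = −0.693 × 0.1725 / 0.75 = −0.159.
- Mild case (15% missing, odds ×1.5): m = −0.405 × 0.1248 / 0.85 = −0.059.

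**Bias with SD = 2.5 points (negative = improvement overstated).**

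| r_b | Strong case, r_f = 0.7 | Mild case, r_f = 0.5 |
|---|---|---|
| 0 | −0.28 | −0.07 |
| 0.2 | −0.20 | −0.04 |
| 0.3 | −0.16 | −0.03 |
| 0.5 | −0.08 | 0.00 |
| 0.7 | 0.00 | +0.03 |

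The baseline correlation drives the result. When it equals the follow-up correlation the bias is zero; if it exceeded it, the sign would change. In SD units the largest figure is 0.7 × 0.159 = 0.11 SD, which carries over to other scales under the same assumptions.

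**Effect on the interval.** In the strong case with r_b = 0.3, the standard error is 2.5 × √(2 × 0.7) / √150 = 0.24. The bias is 0.16 / 0.24 = 0.66 standard errors, so 95% coverage is Φ(1.96 − 0.66) − Φ(−1.96 − 0.66) = 0.90. In the mild case it stays near 0.95.

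**Likelihood model under MAR.** Simulation of 4,000 studies per scenario at r_b = 0.3 gave available-case bias of −0.03 (mild) and −0.16 (strong), against a likelihood bias of 0.001 or less. In the strong case the standard deviation of the estimate fell from 0.241 to 0.220, about 9%.

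**When drop-out depends on the unseen score (MNAR).** A second simulation assumed n=200, SD 2.0, true change −3.8, drop-out of 10/20/30% after 4 months and log-odds of drop-out 1.0 per SD (2,000 studies per scenario). Bias at 24 months:

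| Mechanism and correlations | Available case | Likelihood model |
|---|---|---|
| MAR, r_b 0.2, r_f 0.6 | −0.083 / −0.156 / −0.228 | within 0.005 |
| MAR, all correlations 0.5 | within 0.004 | within 0.003 |
| MNAR, r_b 0.2, r_f 0.6 | −0.101 / −0.200 / −0.305 | −0.047 / −0.097 / −0.158 |
| MNAR, all correlations 0.5 | −0.026 / −0.066 / −0.096 | −0.047 / −0.112 / −0.170 |

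The model removes the bias under MAR, roughly halves it in one MNAR setting and does worse than the available-case mean in the other. With drop-out completely at random both are unbiased and the model is only more precise (0.202 to 0.186 at 20% drop-out with r_b 0.2, r_f 0.6).

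**The case against.** Four objections have force.

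1. **The size is small and unknown.** At r_b = 0.3 the bias is at most 0.16 points on a 0-10 pain scale, its direction depends on who leaves, and the documents supply none of the inputs. This stands, and limits the point to a cheap improvement. It is not a fault that overturns a result.
2. **The exit reasons may break MAR.** An adverse event or device failure can occur after the last recorded score. This stands; the model needs an MNAR check beside it.
3. **The study is mainly descriptive (protocol 9.0) and changing numbers will be visible.** SAP 7 reports n and annotates missing observations, SAP 7.1.1 gives discontinuation reasons, and protocol 4.2.5 seeks final observations at withdrawal. This discloses attrition but adjusts no mean, and the SAP still attaches p-values and a significance threshold to these changes.
4. **The missing-data sentence is not itself at fault.** A mixed model also uses available data without imputation. Agreed: the choice at issue is the per-visit t-test in SAP 7.

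A reader might also infer three stronger things. One is that these means are unbiased only when data are missing completely at random; the equal-correlation rows show otherwise. Another is that a likelihood model is free of the bias in general; the MNAR rows show otherwise. The third is that the problem is larger at interim analyses. There, late visits are absent mainly because of enrolment date. That is administrative, and biases a mean only if early and late enrollers differ, which nothing in the documents shows.

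**Conclusion.** The point holds conditionally. The plan estimates each continuous change in whoever has the visit. This biases later means and the trend if drop-out depends on earlier observed scores and follow-up visits correlate more with each other than with the pre-operative value. Equal correlation would require the pre-operative score to predict month 24 as well as month 12 does, a strong assumption with surgery in between, so some bias under MAR is the more plausible case.

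Under the assumed inputs it runs from 0 to −0.28 points. Only a pain-type score was worked through; for the other endpoints the argument carries over in SD units. The documents do not support a claim that the present tables are biased, or that a model would cure them whatever the reason for drop-out.

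The point covers secondary continuous endpoints. It does not bear on the primary recurrence proportion or the time-to variables.

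**What to change.** In SAP 7 and 7.2.2, items 5 and 10-13:

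- Add a likelihood-based repeated-measures model for each continuous endpoint, with baseline and all visits as responses, visit as a categorical effect and unstructured covariance.
- Prespecify a simpler covariance if the model does not converge or the group is small. Pain, with baseline and seven visits, has 8 × 9 / 2 = 36 covariance parameters, and PROMIS-25 covers only ages 14-17.
- Report the mean change and 95% CI at each visit beside the available-case tables, with n and reasons for missingness by visit. State that the model is valid under MAR.
- Add one delta-shift sensitivity analysis at 24 months. In its simplest form the estimate moves by (share missing) × δ; with 25% missing and δ = 1 point, that is 0.25 points. Show it over a stated range of δ.
- In interim tables, note that late visits contain early enrollers.

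The cost is SAP wording, modest programming and a second estimate per endpoint to explain. No new data are needed, and neither the model nor this form of delta shift imputes values, so protocol 9.5 can stand.
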